# Table 3 Flowchart of PK sampling

| Sample | Sampling time   | V1 | V4 | V6 | V9    |       |       | V12
EoT | FU |   |
|--------|---|----|----|----|-------|-------|-------|------------|----|---|
|        |   |    |    |    | Day 1 | Day 2 | Day 3 | Day 4      |    |   |
|        | Prior to administration   | X  | X  | X  | X     | X     | X     | X          | X  | X |
| PK     | Minimum 6 hours
between samples on
Visit 9, day 2 and day 3 |    |    |    |       | X     | X     |            |    |   |

<sup>1 To be collected prior to trial product administration if dosing occurs on the visit day.

#### 2 INTRODUCTION

### 2.1 Trial Rationale

The purpose of the present phase 3b trial is to investigate the long-term effect on intestinal absorption, nutritional status and the long-term safety of treatment with glepaglutide in patients with SBS.

The efficacy assessments in the ongoing phase 3 program are focused on the effects of glepaglutide on reduction of PS volume and content in patients with SBS with intestinal failure (SBS-IF) with at least 3 days of PS at baseline. The present phase 3b trial serves to investigate the long-term effect of glepaglutide on absorption of fluids, nutrients, electrolytes, and trace elements in patients with SBS with intestinal insufficiency (SBS-II) and SBS-IF employing the gold standard of metabolic balance studies.

# 2.2 Background

Patients with SBS are characterized by reduced intestinal absorptive surface area due to extensive surgical bowel resection or congenital diseases, such as recurrent Crohn's disease or mesenteric vascular disease (1,2,3,4), resulting in decreased absorptive capacity of the gut (5). This causes a reduced uptake of nutrients, fluids, electrolytes, vitamins, and trace elements, leading to difficulties with maintaining metabolic balances when receiving a conventional diet (6). The malabsorption can lead to dehydration, malnutrition, and weight loss if left untreated (7).

Less severely affected SBS patients are able to compensate for their malabsorption by increasing oral intake (hyperphagia) and adapt metabolically or pharmacologically. These patients suffer from intestinal insufficiency (SBS-II). More severely affected patients with intestinal failure (SBS-IF) depend upon the safe and well-adjusted provision of PS of nutrients, fluids, electrolytes, vitamins, and trace elements to maintain body function, growth, homeostasis, and health (8). For those dependent on PS, it is life-sustaining but at the same time associated with life-threatening complications. Among those are catheter-related blood stream infections or sepsis (9), central vein thrombosis, liver damage (10), and renal impairment (11). In addition, the treatment burden of PS is substantial. Often 10-28 liters of PS per week are required. In addition to 10- to 12-hour overnight PS infusions in such patients, additional hours during daytime may be required to compensate for losses. While liberating patients during daytime, night-time infusions disturb sleep and exacerbate the need for nocturnal urination. Adding to the treatment burden, patients on PS often need frequent follow-up checks at the hospital, and for many there is a need for help from a homecare nurse.

Glucagon-like peptide (GLP)-2 is a specific pro-adaptive factor that plays a role in enhancing small intestinal mucosal morphology, function, and integrity both under normal as well as pathophysiological conditions. Exogenous GLP-2 induces significant growth of the small intestinal mucosal epithelium via the stimulation of stem cell proliferation in the crypts and inhibition of apoptosis on the villi (12). This trophic effect of GLP-2 has been observed in numerous species, including humans (13). Additional effects of GLP-2 include inhibition of gastric emptying and gastric acid secretion, stimulation of nutrient absorption, enhancement of intestinal barrier function, and increase in intestinal blood flow (13,14,15,16,17,18,19). The short half-life of native GLP-2 of 5-7 minutes in circulation is a major drawback for its use in a therapeutic setting, and with the approval of teduglutide (US: Gattex®, EU: Revestive®) for the

treatment of adult patients with SBS to improve intestinal absorption of fluids and nutrients, the therapeutic relevance of a GLP-2 analog in SBS has been established.

Glepaglutide is a potent, long-acting GLP-2 analog comprised of 39 L-amino acids, all of which are naturally occurring. Glepaglutide has 9 amino acid substitutions compared with native GLP-2 and a C-terminal structure inducing probe tail consisting of 6 lysines. The sequence similarity of the backbone is about 64% compared with native GLP-2.

When glepaglutide is injected into the subcutaneous (SC) compartment, 2 well-described and functionally active metabolites are formed (ZP18481-34 and ZP18481-35). Under steady-state conditions, the majority of the functional effect on the GLP-2 receptor derives from the main metabolite ZP18481-34, which accumulates during continued use. Thus, the pharmacokinetic (PK) profile and the pharmacological effects of glepaglutide are described and should be understood as a composite effect of the drug substance and its 2 metabolites.

Glepaglutide shows significantly protracted PK. The half-life after SC injection has been shown to differ for glepaglutide and its 2 main metabolites, with the longest half-life observed for the main metabolite ZP18481-34. This suggests that a SC depot is formed and that release of glepaglutide and metabolites from the depot into the systemic circulation is the rate-limiting step that governs the plasma half-life.

The efficacy of 3 weeks of treatment with glepaglutide was demonstrated in a phase 2 trial (trial ZP1848-15073) in a small number of stable SBS patients, where glepaglutide was shown to significantly improve fluid absorption and showed tendencies to improve absorption of macronutrients.

This phase 3b trial is being conducted to confirm the findings from the phase 2 trial, but after long-term treatment and investigate the safety and efficacy of glepaglutide on the amount of PS needed for patients to maintain a satisfactory hydration level.

Based on data from the phase 2 trial (ZP1848-15173) and the PK data from the phase 1 PK trial (ZP1848-16182), one dosing regimen of glepaglutide, 10 mg once-weekly, will be investigated (see Section 4.3 for the rationale for these doses).

For more information on glepaglutide, please refer to the Investigator's Brochure.

### 2.3 Benefit/Risk Assessment

Main benefits and risks are described in the below sections. More detailed information about the known and expected benefits and risks and reasonably expected adverse events (AEs) of glepaglutide may be found in the Investigator's Brochure.

#### 2.3.1 Risk Assessment

#### **Overall Risk Profile**

The results from clinical and non-clinical studies and the safety profile described to date do not give rise to specific safety concerns.

Specifically, the completed non-clinical chronic toxicity program raises no concerns in relation to the extended treatment period of the present trial. The evaluation of chronic toxicity included a study in rats receiving up to 1, 3, and 10 mg/kg/day glepaglutide for 26 weeks and a study in Beagle dogs receiving 0.25, 1, and 5 mg/kg/day glepaglutide for 39 weeks. In both studies, glepaglutide caused a range of findings in the intestinal tract that were attributable to its pharmacological action. In the study in rats, changes occurred in the liver and kidney, which

were likely physiological adaptations to high dose levels of the test material. The systemic noobserved-adverse-effect-level (NOAEL) in this study was therefore determined to 10 mg/kg/day. In the study in Beagle dogs, reduced weight gain was noted in females receiving the highest dose level of 5 mg/kg/day glepaglutide, and the systemic NOAEL in this study was therefore determined to 5 mg/kg/day in males and 1 mg/kg/day in females. Local irritation at the injection sites occurred at all dose levels in both studies. The identified NOAEL exposure level in rats and dogs is ≥86 and ≥48 times higher, respectively, than the expected maximum exposure level in this trial. The carcinogenic potential of glepaglutide has been tested in a mouse and a rat carcinogenicity study. Subcutaneous administration of glepaglutide to CD-1 mice for up to 104 weeks at doses up to 1.0 mg/kg/day, caused a range of findings in the intestinal tract that were attributable to its pharmacological action. There were no neoplastic findings due to treatment demonstrating that ZP1848 was not carcinogenic to the CD-1 mouse. Subcutaneous administration of glepaglutide to Wistar rats at doses up to 2.0 mg/kg/day for 104 weeks caused a range of findings in the intestinal tract that were attributable to its pharmacological action. Mucosal hypertrophy/hyperplasia is considered part of the continuum leading to adenoma and adenocarcinoma formation, and this was considered the cause for the presence of such tumors in the duodenum in a few males given 2.0 mg/kg/day (at exposure approx. 25 times higher than the expected maximum exposure level in this trial. Chronic inflammatory changes at the injection sites seen in both the mouse and the rat carcinogenicity study, resulting from repeated daily subcutaneous injection, occurred at all dose levels and led to an increased incidence of cutaneous pleomorphic fibrosarcomas in males. Pleomorphic fibrosarcomas are considered a group of largely undifferentiated or primitive sarcomas and are the most common type induced in rodents by repeated subcutaneous injection of agents not considered carcinogens (solutions of glucose and other sugars, sodium chloride, certain water-soluble food colourings and surfactants, carboxymethycellulose and macromolecular dextrans (20,21).

Glepaglutide was well tolerated at daily doses of up to 10 mg in the phase 2 trial ZP1848-15073 conducted in SBS patients. Consistent with the clinical setting, the most frequently reported AEs (reported in >20% of patients) in the phase 2 trial were nausea, abdominal pain, abdominal distension, vomiting, stoma complication, fatigue, dizziness, polyuria, decreased appetite, peripheral edema and cough. Treatment-emergent serious adverse events (SAEs) comprised 8 events, with no dose dependency or clustering of events being observed. Injection site reactions were dose dependent, mild to moderate in severity and transient by nature. The most frequently reported symptoms were itching and redness. No deaths were reported in this or any other trials with glepaglutide.

No specific safety issues were raised from the phase 1 clinical trial program; for further details please see the Investigator's Brochure.

In addition to the gastrointestinal tract, there are also GLP-2 receptors in the lung, brain, and hypothalamus (22). So far, clinically significant off-intestinal targeted effects resulting from these additional receptor sites have not been seen.

Experiences with native GLP-2 and teduglutide suggest that expected common AEs for this class of compounds include abdominal pain and distension, injection site reactions, nausea, headache, upper respiratory tract infection, and (in some studies) vomiting, and fluid overload (23).

### **Immunogenicity**

Based on the current non-clinical and clinical knowledge of glepaglutide, the risk of immunogenicity (development of anti-drug antibodies [ADAs]) following administration of glepaglutide is considered high. However, longer-term clinical treatment is required to

investigate whether such a response will be transient or persistent. As no acute or non-acute AEs or effects on PK or pharmacodynamics have been linked to the immune response towards glepaglutide in the completed clinical trials, the effects and potential consequences of the anti-glepaglutide response are so far considered of minor criticality. Glepaglutide ADAs will be monitored in this trial, including their glepaglutide neutralizing potential and reactivity to the main glepaglutide metabolite (ZP18481-34), as well as cross-reaction with native GLP-2.

### **Cardiovascular Safety**

No cardiovascular safety issues have been identified for glepaglutide. A concentration-response analysis of the potential of glepaglutide to cause QT prolongation ruled out any clinically concerning effect at the intended dose level, on which grounds a waiver for a dedicated TQT study was granted by the US Food and Drug Administration (FDA) in April 2018.

Patients with severe and acute cardiac disease are excluded from trial participation (see Section 5.2).

### **Neoplasms**

GLP-2 stimulates development of colonic adenomas in rodent models (24,25,26). Increases in plasma citrulline concentrations as seen with GLP-2 analog treatment might promote growth of existing tumors in patients during long-term treatment. Although the risk of malignancy is hypothetical in humans and colonoscopy can be difficult in these patients, a baseline and a follow-up colonoscopy has been suggested for patients taking GLP-2 analogs who have residual colons (24,25,26). Therefore a screening colonoscopy (within 6 months prior to screening) and a Week 56 colonoscopy is a requirement for patients in the present trial, and patients with a pre-existing recent history of cancer (except for select, treated, and highly curable in situ cancers) are excluded from the trial. If a remnant colon is present, but a colonoscopy may not be appropriate, a computerized tomography (CT) scan, colon capsule endoscopy (CCE) or magnetic resonance imaging (MRI) will suffice at the discretion of the Investigator.

If a remnant colon is present, but not connected to the passage of foods and thereby dormant, a colonoscopy may not be appropriate and in this case a CT scan or MRI (if standard of care at site) will suffice at the discretion of the Investigator to document the absence of concerns regarding malignancy. These are considered adequate precautionary measures. Neoplasms (malignant and benign) are defined as adverse events of special interest (AESIs) for the trial.

#### Risk of Underdosing

The PK results and exposure-response analyzes for glepaglutide substantiates that once-weekly dosing of 10 mg glepaglutide results in glepaglutide concentrations within the therapeutically effective dose range. Regardless, a risk of inadequate dosing in individual patients receiving 10 mg glepaglutide once-weekly cannot be excluded.

### 2.3.2 Benefit Assessment

For the conducted dose-finding trial ZP1848-15073 testing glepaglutide in SBS patients with or without the need of PS, the primary endpoint of change in wet weight of ostomy/diarrhea output ('wet weight output') was chosen as the most direct measure of the impact of glepaglutide on intestinal absorption. The trial met its primary efficacy endpoint by showing statistically significant and clinically relevant reductions in wet weight of ostomy/diarrhea output ('wet weight output') with glepaglutide dosed 1 mg/day (estimated reduction of 592 g/day; p=0.002) and 10 mg/day (estimated reduction of 833 g/day; p=0.0002). Results for wet weight absorption

and urine weight supported the results for the primary endpoint, with statistically significant improvements demonstrated for 1 mg/day and 10 mg/day glepaglutide. In addition, absorption of macronutrients increased in the combined 1+10 mg and 1 mg dose groups, and improvements were observed for absolute absorption of sodium and potassium at the higher glepaglutide dose levels. In conclusion, the phase 2, dose-finding trial of glepaglutide in SBS patients showed consistent and clinically relevant benefit for 1 mg/day and 10 mg/day glepaglutide in improving intestinal function. For further efficacy results please see the Investigator's Brochure for glepaglutide.

Patients receiving glepaglutide treatment in the present phase 3b trial are likely to experience similar or better improvements in intestinal function.

#### 2.3.3 Overall Benefit: Risk Conclusion

In conclusion, the benefit-risk ratio for the proposed glepaglutide treatment regimen is considered favorable for the intended trial population, and potential risks are considered appropriately handled and mitigated.

# 3 OBJECTIVES AND ENDPOINTS

Table 4 Objectives and Endpoints.

| Objectives   | Endpoints  |
|--|--|
| Primary  |  |
| 1. To demonstrate the 24-week effect of glepaglutide on the absorption of fluids.              | 1. Absorption of wet weight/fluids: Change from baseline to Week 24 assessed by 48-hour metabolic balance studies.   |
| Secondary  |  |
| Secondary Objectives   | Key Secondary endpoint:  |
| 1. To assess the effects of glepaglutide on absorption of energy, absorption of the individual | 1. Absorption of energy (oral intake minus fecal excretion):
Change from baseline to Week 24 measured by 48-hour
metabolic balance studies. Energy absorption is measured by
bomb calorimetry.                        |
| macronutrients and absorption of electrolytes.   | Secondary efficacy endpoints:  |
| 2. To evaluate the long-term efficacy of glepaglutide in patients with SBS.                    | 2. Absorption of individual macronutrients (carbohydrates, lipids and proteins): Change from baseline to Week 24 measured by 48-hour metabolic balance studies.  |
| 3. To describe the long-term safety of glepaglutide.   | 3. Absorption of electrolytes (sodium, potassium, calcium and magnesium): Change from baseline to Week 24 measured by 48-hour metabolic balance studies.   |
|  | For patients with SBS-IF only:   |
|  | 4. Weekly PS volume: Change from baseline to Week 12 and 24.   |
|  | 5. Weekly PS macronutrients (carbohydrates, lipids and proteins) and electrolytes (sodium, potassium and magnesium): Change from baseline to Week 12 and 24.   |
|  | Safety endpoints:  |
|  | 6. Treatment-emergent AEs until follow-up at Week 56.  |
|  | 7. Immunogenicity (anti-glepaglutide antibodies, reactivity to ZP1848 1-34 , cross-reactivity to glucagon-like peptide [GLP]-2, glepaglutide neutralizing antibodies) at baseline (W0), Week 4, 12, 24, 52, and 56. |
| Explorative  |  |
| Exploratory objectives   | Exploratory endpoints  |
| 1. To investigate the effect of  | 1. Body weight: Change from baseline to Week 12, 24 and 52.  |
| treatment with glepaglutide on nutritional status, organ function and fluid balance.           | 2. Body composition (lean body mass, fat mass and bone mineral content) by DEXA: Change from baseline to Week 12, 24 and 52.   |
| 2. To investigate the effect of treatment with glepaglutide on patient                         | 3. Citrulline: Change from baseline to Week 12, 24 and 52.   |
| reported outcomes.   | 4. Aldosterone: Change from baseline to Week 12, 24 and 52.  |

- 3. To investigate the microbiome composition of subjects with SBS.
- 4. To investigate the pharmacokinetics of glepaglutide.
- 5. Estimated glomerular filtration rate (eGFR), creatinine clearance and liver function tests: Change from baseline to Week 12, 24 and 52.
- 6. HbA1c: Change from baseline to Week 4, 12, 24 and 52.
- 7. PRO: patient's global impression of change (PGIC). At Week 12, 24 and 52.
- 8. PRO: SBS -impact scale (SBS-I) and EQ-5D-5L. Change from baseline to Week 12, 24 and to Week 52.
- 9. Pharmacokinetic (PK) parameters (t1/2 and Ctrough).
- 10. To investigate the luminal- and mucosae-associated microbiota of patients with SBS from baseline to Week 24.
- 11. Urinary excretion of electrolytes (sodium, potassium, calcium, magnesium) and urea: Change from baseline to Week 24.
- 12. Fluid Composite Effect: Change from baseline to Week 11, 24 and 52.
- 13. Drinking volume during 48-hour periods: Change from Week 24 to 52.

#### For patients with SBS-IF only:

- 14. Weekly PS volume: Change from baseline to Week 52.
- 15. Weekly PS macronutrients (carbohydrates, lipids and proteins) and electrolytes (sodium, potassium and magnesium): Change from baseline to Week 52.
- 16. Weekly days on PS: Change from baseline to Week 12, 24 and 52.

### For patients with SBS-II only:

17. Urine output: Change from baseline to Week 12, 24 and 52.

[figure not shown]
#### 4 TRIAL DESIGN

# 4.1 Overall Design

This is a single-center phase 3b trial investigating the long-term effect on intestinal absorption and nutritional status and long-term safety of treatment with glepaglutide in patients with SBS.

It is planned to enroll a minimum of 6 and a maximum of 16 patients for the trial, where enrollment is defined as receiving trial product.

The overall trial design is presented in Figure 1.

The orange circles represent 48-hour in-house metabolic balance studies. Visits are indicated with lines and the week number from Visit 1 is indicated.

### Figure 1 Overall Trial Design

The trial consists of a screening period, a treatment period and a follow-up period.

After signing informed consent, patients will be screened for initial confirmation of eligibility. The screening procedures should be performed within 3 weeks prior to Visit 1 (baseline).

At Visit 1, eligible patients will complete a 48-hour in-house (admission to the hospital, at site) baseline metabolic balance study as well as other baseline assessments, where after they will start treatment with glepaglutide 10 mg once-weekly for 52 weeks. The treatment period covers 12 visits at the week numbers indicated in Figure 1.

All patients will have in-house stays for 48-hour metabolic balance studies at baseline and at Visit 9; see Figure 1. During the in-house periods, they must follow an individual drinking menu, but may vary the food intake according to their own choice.

All patients will have a 48-hour period scheduled before each Visit (except Visit 1 and 9 where balance studies are done), during which they must record their fluid intake and urine output. During the screening phase, all patients need to construct an individual fixed drinking menu to be kept during all 48-hour "pre-visit" periods until Visit 9. The same individual drinking menu will be followed during both scheduled in-house 48-hour metabolic balance studies (at Visit 1 and 9). After Visit 9, the patients are no longer restricted to a fixed drinking menu during the 48-hour periods, but they should instead drink an amount that reflects their preferred or habitual fluid intake. They must only drink the same fluid items as in the drinking menu and must record their intake as well as their urine output. Patients receiving PS (patients with SBS-IF) will have their PS adjusted based on an algorithm which will be used at each visit (see section 8.2.9).

A follow-up visit will be performed 4 weeks after end of treatment.

For each patient the trial period will be a maximum of 59 weeks.

# 4.2 Scientific Rationale for Trial Design

The purpose of the present phase 3b trial is to investigate the long-term effect on the intestinal absorption, nutritional status and the long-term safety of treatment with glepaglutide in patients with SBS.

The efficacy assessments in the ongoing phase 3 program are focused on the effects of glepaglutide on reduction of PS volume and content in patients with SBS-IF with at least 3 days of PS at baseline. The present phase 3b trial serves to investigate the direct effect of glepaglutide on absorption of fluids, nutrients, electrolytes, and trace elements in patients with SBS-II and SBS-IF.

Balance studies quantify weight, volume, as well as the content of energy, macronutrients and electrolytes of oral intake (i.e. food and fluid intake) and of the output (i.e. ostomy output, diarrhea and urine production). Balance studies are acknowledged as the "gold standard" to measure intestinal function and the methods used have been published (27). Metabolic balance study is a comprehensive method, and the laboratory of the Department of Gastroenterology and Hepatology at Rigshospitalet is one of the few centers of excellence in the world holding the equipment and expertise to perform these metabolic balance studies. The trial site has become internationally recognized for its pioneering role and its significant contribution to evidencebased treatment options within the field of intestinal failure. In a patient group as SBS, having a severe compromised intestinal absorption that may require PS, the ability to quantify intestinal absorptive function of wet weight, energy, macronutrients (carbohydrate, fat, protein), and electrolytes (sodium, potassium, calcium and magnesium), provides the clinician with options to tailor an individual nutritional and medical strategy for patients. Implementing the metabolic balance study in a clinical trial setup is a unique opportunity to test the efficacy of a medical therapy on the intestinal function. The principle of this clinical trial is to perform a "baseline" metabolic balance study leading up to the first administration of trial product. The "treatment" metabolic balance study is then repeated after a period of treatment. In this trial, the primary and key secondary endpoints will be captured after 24 weeks of treatment with glepaglutide 10 mg once-weekly.

Intestinal wet weight absorption is an important clinical outcome for patients with SBS. Efficacy on intestinal wet weight absorption and nutritional status of GLP-2 and its analogs has until this trial been limited to short-term clinical trials of 3-4 weeks treatment periods (28,29). For the first time, this trial will investigate the effect of long-term treatment with a GLP-2 analog on intestinal absorption, nutritional status and long-term safety in patients with SBS. The primary objective of the trial has therefore been chosen as the 24-week effect of glepaglutide on the absorption of fluids. Key secondary endpoint of this trial was chosen as the intestinal absorption of energy (oral intake minus fecal excretion) measured at Week 24 of treatment with glepaglutide.

The documentation of glepaglutide's effects on intestinal energy absorption obtained in this glepaglutide single-center, single-arm, fixed dose, phase 3b trial is expected to directly contribute to the regulatory filing and support the medical communication both pre- and post-launch of the product. During glepaglutide treatment, patients with SBS-IF will have less need of PS and micronutrients. The long-term effects of the reduced amount of PS on body equilibrium, body weight, body composition and other organ functions are unknown.

Patients will be screened to exclude those recently hospitalized more than twice due to SBS or related to PS, those with uncontrolled IBD, those with a history of cancer (except resected cutaneous basal or squamous cell carcinoma and in situ cervical cancer) unless it can be

documented that the patient has been in a disease-free state for at least 5 years and other disorders that may put the patient at an increased risk. Patients with any history of colon cancer are not allowed to enter the trial. Additionally, patients with a remnant colon are required to have a colonoscopy according to local standard practice performed as part of the screening procedures, and at the follow-up visit. If patients had a colonoscopy performed within the last 6 months prior to screening as part of the standard of care of the disease, results from this will be acceptable. If a remnant colon is present, but not connected to the passage of foods and thereby dormant, a colonoscopy may not be appropriate and in this case a CT scan, CCE or MRI will suffice at the discretion of the Investigator to document the absence of concerns regarding malignancy.

During treatment with trial product, patients will be carefully monitored for AEs, vital signs, and laboratory abnormalities. As no acute or non-acute AEs have been linked to the immune response to glepaglutide so far, samples for ADA will be analyzed following the last patient's last visit. Additionally, an internal Safety Committee (see Section 10.1.6) will routinely review safety data to monitor and ensure patient safety.

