<sup>2 Eligibility criteria to be checked prior to initiating 48-hour Metabolic Balance Study.

<sup>3 Also includes patient history of drug and/or alcohol abuse, information on smoking and current alcohol consumption. Concomitant illness to be divided into SBS-related or not.

<sup>4 Pulse rate, blood pressure and body temperature.

<sup>5 Full physical examination at Screening. At the other visits, an abbreviated examination will be performed driven by SBS.

<sup>6 Patients with a remnant colon are required to have a colonoscopy as part of the screening procedures and the follow-up visit (Week 56). Colonoscopy results must be available for Visit 1. Colonoscopies performed up to 6 months prior to screening are acceptable. If a remnant colon is present, but a colonoscopy may not be appropriate, a computerized tomography (CT) scan, colon capsule endoscopy (CCE) or magnetic resonance imaging (MRI) will suffice at the discretion of the Investigator.

| Procedure  | Screening                |                            |    |    |    | Treati | nent Perio | od  |     |     |     |     | ЕоТ | Follow-
up |
|--|--------------------------|----------------------------|----|----|----|--------|------------|-----|-----|-----|-----|-----|-----|---------------|
| Visit  | SCR                      | V1                         | V2 | V3 | V4 | V5     | V6         | V7  | V8  | V9  | V10 | V11 | V12 | FU            |
| Visit day or week  |                          | Day -3 to
day 1
(W0) | W1 | W2 | W4 | W8     | W12        | W16 | W20 | W24 | W32 | W40 | W52 | W56           |
| Time window (days)   | Up to 21 days before V1. |                            | ±2 | ±3 | ±5 | ±5     | ±5         | ±7  | ±7  | ±7  | ±14 | ±14 | ±14 | ±14           |
| Visit type: Site (S), In-house (I)   | S                        | I                          | S  | S  | S  | S      | S          | S   | S   | I   | S   | S   | S   | S             |
| Serum pregnancy test (hCG)
(WOCBP only)   | X                        | X                          |    |    | X  | X      | X          | X   | X   | X   | X   | X   | X   | X             |
| FSH    | X                        |                            |    |    |    |        |            |     |     |     |     |     |     |               |

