### 8.1.6 Colonoscopy

Patients with a remnant colon are required to have a colonoscopy as part of the screening procedures and the follow-up visit (Week 56). Colonoscopy results must be available for Visit 1. Colonoscopies performed up to 6 months prior to screening are acceptable. If a remnant colon is

present, but a colonoscopy may not be appropriate, a CT scan, CCE or MRI will suffice at the discretion of the Investigator.

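### Section 4.2 accepts colon capsule endoscopy for a remnant colon that is off the food route, a segment a swallowed capsule cannot view (minor safety-rule error)

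*Protocol*

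**What the plan says.** The Protocol sets out substitutes for colonoscopy in several places.

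- **Section 4.2**, for a remnant colon "not connected to the passage of foods and thereby dormant, a colonoscopy may not be appropriate and in this case a CT scan, CCE"; MRI completes the list. The purpose is given in the same sentence: "CCE or MRI will suffice at the discretion of the Investigator to document the absence of concerns regarding malignancy".
- **Section 2.3.1, Neoplasms, dormant-colon sentence**, for the same anatomy and purpose: "in this case a CT scan or MRI (if standard of care at site) will suffice at the discretion of the Investigator".
- **Section 2.3.1, Neoplasms, general paragraph**, where colonoscopy may not be appropriate: CT, "colon capsule endoscopy (CCE) or magnetic resonance imaging (MRI) will suffice at the discretion of the Investigator".
- **Table 1 footnote 6** (Section 1.2): "If a remnant colon is present, but a colonoscopy may not be appropriate, a computerized tomography (CT) scan, colon capsule endoscopy (CCE") or MRI.
- **Section 8.1.6**, for a remnant colon that is "present, but a colonoscopy may not be appropriate, a CT scan, CCE or MRI will suffice at the discretion of the Investigator".

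Footnote 6 and Section 8.1.6 also require the result to be available for Visit 1, accept a colonoscopy from the 6 months before screening, and repeat the examination at Week 56.

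**The concern.** Section 4.2 defines the segment by the fact that food does not pass through it, and then accepts an examination that depends on the same route. A capsule that is swallowed cannot reach that segment, so it can give no evidence about malignancy there.

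The check has a stated reason: "GLP-2 stimulates development of colonic adenomas in rodent models". Section 2.3.1 adds that raised citrulline might promote growth of existing tumors. Neoplasms are adverse events of special interest (Section 8.4.6), any history of colon cancer excludes a patient (Section 5.2, criterion 12), and any malignancy stops treatment (Section 7.1). Under the Section 4.2 wording, the check could be recorded as done before 52 weeks of dosing, and again at Week 56, without the segment having been viewed.

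**Working it through.** No arithmetic applies and the plan states no figure on this point. The check is a comparison of every statement that lists substitutes for colonoscopy.

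| Place in Protocol | Names the disconnected colon? | Substitutes listed |
|---|---|---|
| Section 4.2 | Yes | CT, CCE, MRI |
| Section 2.3.1, dormant-colon sentence | Yes | CT, MRI (if standard of care at site) |
| Section 2.3.1, general paragraph | No | CT, CCE, MRI |
| Table 1 footnote 6 | No | CT, CCE, MRI |
| Section 8.1.6 | No | CT, CCE, MRI |

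1. There are 5 statements, of which 2 name the disconnected colon and 3 are general (2 + 3 = 5).
2. Of the 2 that name it, 1 accepts CCE (Section 4.2) and 1 does not list it (Section 2.3.1). The anatomy and purpose are the same. Apart from the standard-of-care condition in Section 2.3.1, CCE is the only difference between the two lists.
3. The 3 general statements allow CCE wherever colonoscopy may not be appropriate. They are not wrong for a colon in the food stream. However, Sections 2.3.1 and 4.2 both give the disconnected colon as a case where colonoscopy may not be appropriate, so that case falls under the general rule and nothing takes it out again.
4. The remaining step is whether CCE can serve the purpose. Two premises are needed: the segment is off the food route (the Protocol's own definition), and the capsule is swallowed (ordinary meaning of the term, not stated in the documents). If both hold, the capsule does not enter the segment and cannot document anything about it.
5. On size, Section 4.1 caps enrollment at 16. Neither document says how many patients would have a disconnected colon, and the number could be zero. No share of patients or examinations can be derived.

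**The case against.** The strongest reply is that this is a wording slip in a rationale section and is unlikely to mislead anyone. CCE is permitted, not required. CT and MRI stand in the same sentence. The choice is the Investigator's, and the substitute has to serve the stated purpose, which a capsule that misses the segment would not do. The only site is a gastroenterology department that Section 4.2 describes as internationally recognized in intestinal failure. All of this stands and keeps the likelihood of harm low. It does not make the statement that CCE suffices correct. The operational text does not repair it either: footnote 6 and Section 8.1.6 list CCE with no exclusion.

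A reader might also infer that Section 2.3.1 forbids CCE for this anatomy, so that the Protocol plainly contradicts itself. The text does not go that far. The dormant-colon sentence says that CT or MRI is enough, not that nothing else is, and the general paragraph before it lists CCE in terms that literally cover a dormant colon. Nor does "These are considered adequate precautionary measures" show that the sponsor meant to limit this case to CT or MRI. It closes the whole Neoplasms discussion, including the colonoscopies, the cancer exclusion and the substitutes in which CCE appears. What remains is a difference between two parallel sentences, one of which names an examination that cannot do the job.

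**Conclusion.** The concern holds as a minor error in a safety rule. For a remnant colon off the food route, Section 4.2 accepts an examination that cannot view the segment, its counterpart in Section 2.3.1 does not list that examination, and no other statement excludes it. The conclusion rests on one premise from outside the documents, that a colon capsule is swallowed.

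The size is 1 of the 2 sentences on this anatomy, plus 3 general statements that lack an exclusion, in a trial of at most 16 patients with an unknown number affected. No efficacy endpoint, estimand or efficacy analysis is touched.

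Two stronger conclusions might be drawn and are not supported. One is that patients will go unexamined: the documents show only that the rule would permit it. The other is that CT or MRI should become mandatory for a disconnected colon: both sentences say only that colonoscopy may be inappropriate, so colonoscopy remains available where it is feasible.

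**What to change.** 1. In Section 4.2, delete CCE from the dormant-colon sentence, leaving CT and MRI.
2. In Table 1 footnote 6 and Section 8.1.6, and in the general paragraph of Section 2.3.1 for consistency, add: *CCE must not be used as the substitute for a colon segment not connected to the passage of foods.*

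The added line bars one examination for one anatomy and imposes nothing in its place. Colonoscopy where appropriate, CT or MRI at the Investigator's discretion, and CCE for colon in the food stream all stay as now. The standard-of-care condition in Section 2.3.1 needs no change.

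The cost is one abbreviation deleted and one sentence added in three places at the next amendment. There is no new procedure, visit or data item, because CT and MRI are already listed.
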